4.3.2.2 SUBJECT CLASSIFICATION FOR NAb – OVERALL AND BY CYCLE

ADA confirmed positive samples were further evaluated in the NAb assay. All ADA negative samples were thus not analysed in the NAb assay but should be considered per default as NAb negative in the analysis.

If a NAb sample is not reported, the NAb sample status will be NAb unevaluable.

All samples evaluated in the NAb assay will be scored as NAb positive, NAb negative or NAb unevaluable by the laboratory. Based on these results, the patients will be categorized based on their baseline and post-baseline sample status as detailed in following table.

Subject NAb classification	Highest ^a post baseline ^b		
	NAb sample status		
	NAb negative	NAb positive	NAb not evaluable
Baseline NAb sample status			
NAb negative	baseline neg – post-baseline neg	baseline neg – post-baseline pos	NAb unevaluable
NAb positive	baseline pos - post-baseline neg	baseline pos – post-baseline pos	NAb unevaluable
NAb not evaluable	NAb unevaluable	NAb unevaluable	NAb unevaluable

^a Highest sample status in order: (from low to high): NAb unevaluable, NAb negative, NAb positive.

^b For the overall NAb subject classification, the highest post baseline sample status over all cycles is used for comparison with the baseline NAb sample status.

For the cycle NAb subject classification, the highest post baseline sample status within the cycle is used for comparison with the baseline NAb sample status.

NAb unevaluable patient = patient classified as NAb unevaluable or with missing baseline NAb sample or without post-baseline NAb samples

NAb incidence=percentage of patients with subject classification ‘baseline neg – post-baseline pos’ and ‘baseline pos – post-baseline pos’ (denominator: number of evaluable patients).

NAb prevalence=percentage of patients with subject classification ‘baseline neg – post-baseline pos’, ‘baseline pos – post-baseline pos’ or ‘baseline pos – post-baseline neg’. (denominator: number of evaluable patients).

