2.2.2 Baseline and change from baseline

Two baselines are defined:

- Baseline is the last available value prior to first administration of efgartigimod in the first cycle in 1705.
- CnB: Cycle n Baseline i.e. last available value prior to first administration of efgartigimod in cycle n, with n=1, 2, 3, etc..

Note: for MG-ADL and QMG, all assessments on the day of first administration of the IMP in cycle n are considered in the baseline selection, also those post-administration.

Change can be calculated from baseline or CnB. Note: baseline coincides with C1B. Baseline will be considered for analyses that assess across all cycles and the CnB will be used for analyses restricted to a specific cycle, n.

Change for safety parameters will be calculated from baseline only.

For efficacy and PD, a (percent) change can be calculated from baseline or CnB, according to the analysis.

	Statistical Analysis Plan	
ARGX-113-1705	Final Analysis	Final 1.0 of 20SEP2022

Change from baseline at time point t = value at time point t – baseline value.

Percent change from baseline at time point t = (actual value at time point t -baseline value)*100/baseline value.

Change from CnB at time point t = value at time point t – CnB value.

Percent change from CnB at time point t = (actual value at time point t - CnB value)*100/CnB value.

2.2.3 *Relative day*

Relative days in the period (ADYP) will be calculated according to the following rule:

- Concerned date < reference date: ADYP = concerned date – reference date
- Concerned date ≥ reference date: ADYP = concerned date – reference date + 1

The reference date is the date of first administration of study drug in the specific period, except for assessments in ITP0, for which the date of informed consent in 1705 will be taken as reference date.

2.2.4 *Analysis visits*

All assessments (from first ARGX-113-1705 cycle on), including unscheduled assessments, will be allocated to analysis windows. Tables and listings will present the analysis windows as defined below, not the CRF visits. Allocation of assessments will be done using their relative day in the period (see section 2.2.3).

Table 4: Analysis visits

Phase/Period	Analysis window	Target ADYP	Lower limit ADYP	Upper limit ADYP
Treatment/ cycle n (=Treatment Period n + ITP_n)				
	CnB	1	-INF	1*
	Week 1	8	1*	11
	Week 2	15	12	18
	Week 3	22	19	35
	Week 7	50	36	63
	Week 7 + (4*x)	50 + (x*28)	50 + (x*28) - 14	50 + (x*28) + 13

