4.3 ANTI-DRUG ANTIBODIES

4.3.1 Available data

During part A of the study, presence of anti-drug antibodies (ADA) to efgartigimod is measured at the roll-over visit, at baseline and week 3 of each cycle and at EoA.

During part B, ADA is measured at baseline and EoS only.

[figure not shown]
ADA samples are analysed in a 3-tiered approach:

- All samples are evaluated in the ADA screening assay and are scored ADA screening positive or negative.
- If a sample scored ADA screening positive, it is further evaluated in the confirmatory assay and is scored confirmed positive (positive immunodepletion) or confirmed negative (negative immunodepletion).
- If a sample is scored as confirmed positive, the samples are further characterized in the ADA titration assay (to determine titer) and are also further analysed in the Nab assay to confirm neutralizing activity (positive or negative).

If available, a titer result will be reported for the ADA confirmed positive samples. However, a titer result is not always available:

- In case the ADA confirmed positive sample could not be run in the titration assay (e.g. due to insufficient sample volume/quality to perform the titer analysis) the result will be described as ‘positive immuno-depletion’ and the sample should be considered as ADA positive.
- If a sample is negative in the titration assay, it will be reported as ‘negative titer’ but the sample should be considered as 'ADA positive' since it was confirmed positive in the second tier.
- If a sample is not reported or reported as ‘positive screen’, the ADA sample status is ADA unevaluable.

An overview of this 3-tiered approach and all possible ADA sample results that will be reported by the laboratory is given below. From these reported ADA sample results a final ADA sample status needs to be derived during the statistical analysis, as presented in the final column (Final ADA Outcome):

^a Missing screen includes the following terms (reported as reason not done): NA (not analysed), NR (no result), NS (no sample) and SL (sample lost). More details can be found in the IS data transfer agreement from SGS France to SGS SD office.

^b 'positive titer' is reported in case it was not possible to retrieve a numeric value.

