4.3.2 Derivation rules

4.3.2.1 SUBJECT CLASSIFICATION FOR ADA – OVERALL AND BY CYCLE

Table below gives an overview of how the ADA subject classification will be derived, starting from the patient baseline ADA sample status.

Subject ADA classification	Highest ^c post-baseline ^d sample status				
	ADA negative	ADA positive (missing titer ^a)	ADA positive (negative titer ^b or numeric titer value)		ADA not evaluable
Baseline ADA sample status					
ADA negative	ADA negative	Treatment Induced ADA	Treatment Induced ADA		ADA unevaluable
ADA positive (missing titer ^a)	Treatment Unaffected ADA	ADA unevaluable	ADA unevaluable		ADA unevaluable
ADA positive (negative titer ^b or numeric titer value)	Treatment Unaffected ADA	ADA unevaluable	titer < 4 x baseline titer: Treatment Unaffected ADA	titer ≥ 4x baseline titer: Treatment Boosted ADA ^e	ADA unevaluable
ADA not evaluable	ADA unevaluable	ADA unevaluable	ADA unevaluable		ADA unevaluable

^c Samples with missing titer have as reported ADA result 'positive immunodepletion' or 'positive titer';
^d Results reported as 'negative titer', i.e. titer value <1 will be set to value of 1;
^e Highest sample status, with order: (from low to high): ADA unevaluable, ADA negative, ADA positive (missing titer /positive immunodepletion), ADA positive with titer < 1 ('negative titer' as reported ADA result, titer value set to 1), ADA positive with titer ≥ 1 (i.e. positive titer and selecting the sample with highest titer)
^f For the overall ADA subject classification, the highest post baseline sample status over all cycles is used for comparison with the baseline ADA sample status.
 For the cycle ADA subject classification, the highest post baseline sample status within the cycle is used for comparison with the baseline ADA sample status.
^g Note: Four-fold difference in titer values is considered significant in case a twofold serial dilution is applied (=two times the dilution factor) (reference to Shankar et al., 2014).

ADA evaluable patient = patient classified as any of following categories: ADA negative, treatment unaffected ADA, treatment induced ADA, treatment boosted ADA.

ADA unevaluable patient = patient classified as unevaluable or with missing baseline ADA sample or without post-baseline ADA samples.

In case no ADA data is available at all, the participant cannot be classified.

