ADA incidence = percentage of patients with treatment-induced or treatment-boosted ADAs (denominator: number of evaluable patients). Treatment-unaffected ADAs are not taken into account.

ADA prevalence = percentage of patients with treatment-unaffected ADA, treatment-induced ADA or treatment-boosted ADA (denominator: number of evaluable patients).

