4.3.3 Statistical analysis

Analysis will be done on all patients.

Frequency tabulations (number and percentages) will be provided with ADA negative/positive/unevaluable samples per analysis visit.

	Statistical Analysis Plan	
ARGX-113-1705	Final Analysis	Final 1.0 of 20SEP2022

Frequency tabulations (number and percentages) will be provided by cycle and overall on:

- patients per ADA subject category
- prevalence and incidence of ADA
- ADA unevaluable patients
- ADA baseline positive/negative samples

For details on the definitions, see the above section [4.3.2.1](#).

The ADA subject category of the applicable cycle will be used for all tables.

ADA titer values will be summarized by means of descriptive statistics by overall ADA subject category.

The above frequency tabulations will be repeated for NAb assay using the definitions as defined in section [4.3.2.2](#).

In addition, a frequency tabulation (number and percentages) will be provided of NAb positive patients within the overall ADA subject category (treatment-unaffected ADA, treatment-induced ADA, treatment-boosted ADA, ADA negative and ADA unevaluable).

	
Statistical Analysis Plan
	

ARGX-113-1705
	
Final Analysis
	
Final 1.0 of 20SEP2022

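### NAb incidence counts patients already NAb positive at baseline without asking for an increase, so among NAb-evaluable patients it measures post-baseline NAb positivity

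*SAP*

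**What the plan says.** SAP section 4.3.2.2 classifies each patient by baseline NAb status and by the highest NAb status after baseline. The definition of incidence reads: "NAb incidence=percentage of patients with subject classification ‘baseline neg – post-baseline pos’ and ‘baseline pos – post-baseline pos", with NAb-evaluable patients as denominator. Prevalence uses the same two classes and adds patients who were positive at baseline and negative afterwards.

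SAP section 2.2.2 fixes the reference point: "Baseline is the last available value prior to first administration of efgartigimod in the first cycle in 1705". NAb is tested only on samples that already tested positive for ADA. Section 4.3.2.2 states "ADA confirmed positive samples were further evaluated in the NAb assay", and section 4.3.1 says that confirmed positive samples "are also further analysed in the Nab assay to confirm neutralizing activity".

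The ADA rules in section 4.3.2.1 work differently. For a patient with titers at baseline and afterwards, the table gives "titer < 4 x baseline titer: Treatment Unaffected ADA", and a titer of at least four times baseline makes the patient treatment-boosted. ADA incidence counts induced and boosted patients, and the SAP adds: "Treatment-unaffected ADAs are not taken into account".

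On output, section 4.3.3 says "The above frequency tabulations will be repeated for NAb assay using the definitions as defined in section" 4.3.2.2, and that "a frequency tabulation (number and percentages) will be provided of NAb positive patients within the overall ADA subject category". The incidence figure goes into Table 14.2.4.5. Section 2.4.3 has tables shown per treatment, with the efgartigimod-efgartigimod group before the placebo-efgartigimod group.

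**The concern.** Incidence normally means something that appears, or at least rises, during the observation period. The NAb definition requires neither. Two adjacent subsections use the same word for different things: a patient can be left out of ADA incidence as treatment-unaffected and still be counted in NAb incidence. The SAP gives no reason for the difference.

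The design makes this more than a matter of wording. Patients who received efgartigimod in 1704 could already be NAb positive at the 1705 baseline. Because results are shown by 1704 treatment, NAb carried in from 1704 would fall in the efgartigimod-efgartigimod column. It could then be read as a difference between the columns in newly formed NAb. In the by-cycle part of the table, a patient who is positive at baseline and stays positive is counted as incident in every cycle with a positive sample.

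**Working it through.** The plan gives no NAb counts, so there is no figure to reproduce. The check has three steps.

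**1. What the numerator counts.** The four evaluable classes of the NAb table in SAP section 4.3.2.2, with the SAP definitions applied:

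| Baseline | Highest post-baseline | In SAP incidence | In SAP prevalence | Newly positive |
|---|---|---|---|---|
| negative | negative | no | no | no |
| negative | positive | yes | yes | yes |
| positive | negative | no | yes | no |
| positive | positive | yes | yes | no |

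The incidence column says yes exactly where the post-baseline status is positive. The other five cells of the table have an unevaluable baseline or post-baseline status and count in neither measure. Prevalence exceeds incidence only by the positive-to-negative patients.

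**2. What ADA class a NAb positive-to-positive patient can have.** Only ADA-confirmed-positive samples reach the NAb assay, so such a patient is ADA positive both at baseline and afterwards. Under the table in SAP section 4.3.2.1:

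- baseline titer missing, post-baseline titer missing: unevaluable
- baseline titer missing, post-baseline titer available: unevaluable
- baseline titer available, post-baseline titer missing: unevaluable
- both available, ratio below 4: treatment-unaffected
- both available, ratio 4 or more: treatment-boosted

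None of the five outcomes is treatment-induced, and only the last enters ADA incidence. All five enter NAb incidence.

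**3. Size.** Let c be the negative-to-positive patients, k the positive-to-positive patients and N the NAb-evaluable patients. N is at most 167 (SAP section 1.3).

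SAP incidence − negative-to-positive incidence = (c + k)/N − c/N = k/N.

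At N = 167:

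- k = 0: 0
- k = 1: 1/167 = 0.60%
- k = 2: 2/167 = 1.20%
- k = 5: 5/167 = 2.99%

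With a smaller N each patient weighs more. In a single treatment column of assumed size 100, 84 or 60, one patient adds 1.00, 1.19 or 1.67 points.

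Illustration with assumed counts c = 5 and N = 167. SAP incidence (5 + k)/167 is 2.99%, 4.19%, 5.99% and 8.98% for k = 0, 2, 5 and 10. Negative-to-positive incidence stays at 5/167 = 2.99% throughout.

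**The case against.** **There is no NAb titer.** The assay is scored only positive, negative or unevaluable, so the fourfold rule cannot be carried over. ADA incidence itself includes some baseline-positive patients, namely the boosted ones. With a yes/no assay the SAP must count either all positive-to-positive patients or none, and counting none would drop any who were boosted. This stands as a reason to keep these patients visible. It does not justify calling every persistent positive incident when the result shows no increase.

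**The detail is already planned.** This is largely right. Section 4.3.3 repeats the subject-category tabulation for NAb, so the count in each of the four classes will be reported by cycle and overall. Table 14.2.4.6 and Listing 16.2.12.1 add ADA information. A reader might infer that the SAP hides the positive-to-positive patients, and the documents do not support that. What section 4.3.3 does not specify is a split of that class by ADA category. The row labelled incidence in Table 14.2.4.5 also remains as defined.

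**The harm is conjectural.** The documents contain no table shell and no NAb data. A footnote could state the definition, and the planned baseline tabulation by treatment would show an imbalance. This limits the severity but does not make the label correct.

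**The alternative has an imperfect denominator.** Baseline positives cannot become negative-to-positive. With c = 5, N = 167 and an assumed 2 positive-to-negative patients, restricting the denominator to baseline negatives gives 5/(167 − k − 2), that is 3.03% at k = 0 and 3.23% at k = 10, against 2.99%. Under these assumed counts that is a small difference, and keeping all evaluable patients matches the SAP's convention.

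**Conclusion.** The definition does not measure incidence as written. Among NAb-evaluable patients it equals post-baseline NAb positivity, and it exceeds a negative-to-positive measure by k/N, at least 0.6 points per positive-to-positive patient. That part is certain because it follows from the SAP's own classes. Whether any reported figure would change depends on k, which the documents do not give and which may be zero.

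Three stronger readings might be inferred and are not supported:

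- *That every patient with a positive post-baseline sample counts.* A patient whose baseline is missing or unevaluable is NAb unevaluable and is not counted.
- *That k/N caps the gap to an induced-or-boosted measure.* Let b be the boosted patients among the k. Let u be the negative-to-positive patients who were ADA positive but NAb negative at baseline and are classed as treatment-unaffected or ADA unevaluable. The gap over the same N is (k − b + u)/N, which exceeds k/N whenever u is larger than b.
- *That NAb from 1704 does inflate the efgartigimod-efgartigimod column.* The design allows it, but no data in the documents show it.

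The severity is minor. One descriptive table is affected, Protocol section 3.3 names ADA incidence and prevalence and not NAb incidence, and Protocol section 8 makes all evaluation essentially descriptive.

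**What to change.** In SAP section 4.3.2.2, define NAb incidence as the negative-to-positive class only, over NAb-evaluable patients. Split the positive-to-positive count already planned under section 4.3.3 by ADA class (boosted, unaffected, unevaluable), so that possible boosting can still be seen.

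If the sponsor prefers the current numerator, label it post-baseline NAb positivity in section 4.3.2.2 and Table 14.2.4.5, and do not call it incidence.

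Neither option makes the NAb figure equivalent to ADA incidence. A negative-to-positive patient can still be treatment-unaffected for ADA, and the two denominators differ. A footnote should say so.

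The cost is one line of SAP wording, one numerator and one split of an existing count, or a label change alone. No new data are needed and no ADA table changes.

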4.3.3 Statistical analysis

Analysis will be done on all patients.

Frequency tabulations (number and percentages) will be provided with ADA negative/positive/unevaluable samples per analysis visit.

	Statistical Analysis Plan	
ARGX-113-1705	Final Analysis	Final 1.0 of 20SEP2022

Frequency tabulations (number and percentages) will be provided by cycle and overall on:

- patients per ADA subject category
- prevalence and incidence of ADA
- ADA unevaluable patients
- ADA baseline positive/negative samples

For details on the definitions, see the above section [4.3.2.1](#).

The ADA subject category of the applicable cycle will be used for all tables.

ADA titer values will be summarized by means of descriptive statistics by overall ADA subject category.

The above frequency tabulations will be repeated for NAb assay using the definitions as defined in section [4.3.2.2](#).

In addition, a frequency tabulation (number and percentages) will be provided of NAb positive patients within the overall ADA subject category (treatment-unaffected ADA, treatment-induced ADA, treatment-boosted ADA, ADA negative and ADA unevaluable).

	
Statistical Analysis Plan
	

ARGX-113-1705
	
Final Analysis
	
Final 1.0 of 20SEP2022

5. SAFETY ANALYSES

5.1 ADVERSE EVENTS

5.1.1 *Available data*

Adverse events (AEs) are coded into system organ classes and preferred terms using the MedDRA version 24.1 (SEP2021). AEs were graded using the National Cancer Institute (NCI) Common Terminology Criteria for Adverse Events (CTCAE) version 5.0. For each AE, start and stop date/times are collected as well as severity, a seriousness flag, treatment relatedness, relatedness to procedures, action taken towards the study drug and outcome.

5.1.2 *Derivation rules*

Based on their start date/time, AEs will be allocated to the analysis period during which they started. Each AE will therefore be reported in only one period. Periods are defined in section 2.2.1. In case the AE start date/time is incomplete or missing and the AE could consequently be allocated to more than one period, AE will be allocated to the first possible cycle unless the available parts of the AE start or stop date/time provide evidence the assessments did not occur during that period.

Event rates per patient years of follow-up (PYFU) will be defined as the number of events divided by the sum of follow-up time (i.e. duration of treatment phase) of all participants per treatment expressed in years.

A death case is defined as an AE with outcome ‘fatal’.

Adverse events of special interest will be defined using MedDRA SOC ‘Infections and infestations’.

Infusion-related reactions (IRR) will be defined as all AEs with a MedDRA preferred terms that are listed in either:

- MedDRA Hypersensitivity SMQ broad selection
- MedDRA Anaphylactic reaction SMQ broad selection
- MedDRA extravasation events (injections, infusions and implants) SMQ broad selection, excluding implants

AND occurring within 48 hours of an infusion, or within 2 days in case no AE start time is available.

An AE for which the study drug was discontinued is defined as an AE with action taken ‘drug withdrawn’.

Treatment-relatedness will be dichotomised as follows in tables:

- Treatment-related: related, probably related, possibly related or missing
- Not treatment-related: not related, unlikely related, not applicable

	
Statistical Analysis Plan
	

ARGX-113-1705
	
Final Analysis
	
Final 1.0 of 20SEP2022

AE onset and duration will be calculated as follows when start and stop dates are fully known

- AE onset day (vs. first administration)
 - AE start date \geq date of first administration: AE start date – date of first administration + 1 day
 - AE start date $<$ date of first administration: AE start date – date of first administration
- AE onset day (vs. start of period) = AE start date – analysis period start date + 1 day
- AE duration (days) =
 - AE end date – AE start date + 1 day
 - study discontinuation date – AE start date + 1 day (when the AE start date is fully known but the AE is not resolved at the end of the study)
 In this case the duration will be presented as “>x days”.

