2.2 PHASES, PERIODS AND TIME POINTS

2.2.1 *Phases and periods*

All events and assessments will be allocated to phases and periods (see Table 1). A patient can start in 1705 in an inter-treatment period or in a cycle, depending on the patient status regarding the need for (re-)treatment upon roll-over. Each period following ITPO coincides with a cycle and includes the 4 administrations of efgartigimod and the inter-treatment period (ITP) visits. The length of the ITP is patient specific and can differ between the different periods. The number of patients may decline for each subsequent cycle.

	Statistical Analysis Plan	
ARGX-113-1705	Final Analysis	Final 1.0 of 20SEP2022

Table 1: phase/period definition

Phase	Period	Start	End
Treatment	ITP0	Earliest of (date of signing the informed consent form (ICF) and date of roll-over), with 00:00 added as time part.	First administration date/time in cycle 1 – 1 minute
	Cycle 1	First administration date/time in cycle 1	First administration date/time in next cycle – 1 minute or if last cycle: date of last contact, with 23:59 added as time part
	Cycle n	First administration date/time in cycle n	First administration date/time in next cycle – 1 minute or if last cycle: date of last contact, with 23:59 added as time part
	Cycle x	First administration date/time in cycle x	Date of last contact, with 23:59 added as time part

AEs and concomitant medications will be allocated to phases and periods as described in sections 5.1.2 and 3.5.2 respectively. All other assessments will be allocated to phases and periods based on the assessment date/time.

In case of (partially) missing date/time fields disabling allocation or date(time) equal to dosing date(time), information from visit label and protocol schedule of assessments (SoA) will be used to allocate to the correct period. If this is not possible, assessments will be allocated to the first possible cycle (not ITP0) unless the available parts of the assessments start or stop date/time provide evidence the assessments did not occur during that period.

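### An adverse event dated on the first infusion day of cycle 2 or later, with no onset time, is tabulated in the previous cycle even if it began after the infusion

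*SAP*

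**What the plan says.** SAP 2.2.1 Table 1 starts a cycle at "First administration date/time in cycle n" and ends the one before it at "First administration date/time in next cycle – 1 minute". The calendar day of re-dosing therefore belongs partly to each cycle.

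For AEs, SAP 5.1.2 begins: "Based on their start date/time, AEs will be allocated to the analysis period during which they started". If the start is incomplete or missing and several periods are possible, the rule is: "AE will be allocated to the first possible cycle unless the available parts of the AE start or stop date/time provide evidence" that it did not occur in that period.

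The same section foresees AEs without a time. An infusion-related reaction is an AE with a listed preferred term and "occurring within 48 hours of an infusion, or within 2 days in case no AE start time is available".

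Other data have a tie-break. Where a date is incomplete or equals a dosing date, SAP 2.2.1 says that "information from visit label and protocol schedule of assessments (SoA) will be used to allocate to the correct period". That paragraph does not govern AEs: "AEs and concomitant medications will be allocated to phases and periods as described in sections 5.1.2 and 3.5.2 respectively". Section 5.1.2 has no equivalent.

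By-cycle AE reporting is planned in Protocol 4.2 and 8.4.1 and in SAP 5.1.3. SAP 2.4.1 takes the patients in each cycle as the denominator.

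**The concern.** The onset-time field decides the cycle only on the re-dosing day, and there the SAP resolves a blank in one direction. A post-infusion event is credited to the cycle that has just ended. The same event can be classed as a reaction to cycle n's infusion and counted among the reactions of cycle n-1.

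Because the error has one direction, it does not average out across cycles. It adds to cycle 1 and takes from each patient's last cycle. Readers of a re-treatment extension will look at whether AEs and infusion reactions become less frequent with repeated cycles, and this misallocation pushes towards that pattern. The onset day counted from period start (SAP 5.1.2) is wrong for the same events.

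**Working it through.** **Step 1. Apply the rule to AEs with a complete date and no time.** Inputs: Table 1 boundaries (SAP 2.2.1) and the allocation rule (SAP 5.1.2).

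| AE date | Periods possible | Allocated to |
|---|---|---|
| Cycle 1, infusion 1 | ITP0, cycle 1 | cycle 1 (ITP0 is not a cycle) |
| Cycle 2, infusion 1 | cycles 1, 2 | cycle 1 |
| Cycle 3, infusion 1 | cycles 2, 3 | cycle 2 |
| Any cycle, infusions 2 to 4 | that cycle only | that cycle |

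An untimed event on the first dosing day of cycle 1 is thus kept with that infusion. The same event on any later re-dosing day is not.

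**Step 2. Test the evidence clause.** Take an infusion at 10:00. A known stop at 20:00 that day does not exclude the earlier cycle, since onset before 10:00 remains possible. A stop before 10:00 confirms the earlier cycle. Only start-time information, such as a recorded 14:00, would move the event to cycle n, and that is the item that is missing. The clause does not mention relatedness, reaction status or closeness to the infusion.

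**Step 3. Onset day, with invented dates.** Cycle 1 starts on 11 January 2020 and cycle 2 on 11 March 2020; the AE is dated 11 March with no time. The interval is 20 + 29 + 11 = 60 days. Under the rule, onset day in period = 60 + 1 = 61 (cycle 1). If allocated to cycle 2, it is 0 + 1 = 1.

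**Step 4. Illustrative size. All inputs are assumed; none is in the documents.** Five cycles with N = 100, 80, 60, 40, 20 patients; true post-infusion AE incidence on the first infusion day r = 10% in every cycle; a share m with no time; each shifted event falls in a patient not otherwise counted in the receiving cycle and with no other event in the cycle it leaves.

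Displayed percentage in cycle k = [r × N(k) × (1 − m) + r × m × N(k+1)] / N(k). The factor (1 − m) is dropped for cycle 1, which loses nothing, and the second term is dropped for cycle 5, which gains nothing.

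For m = 30%:
- cycle 1: (10 + 2.4)/100 = 12.4%
- cycle 2: (5.6 + 1.8)/80 = 9.25%
- cycle 3: (4.2 + 1.2)/60 = 9.0%
- cycle 4: (2.8 + 0.6)/40 = 8.5%
- cycle 5: 1.4/20 = 7.0%

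| m | C1 | C2 | C3 | C4 | C5 | Events in total |
|---|---|---|---|---|---|---|
| 0% | 10.0 | 10.0 | 10.0 | 10.0 | 10.0 | 30 |
| 10% | 10.8 | 9.75 | 9.7 | 9.5 | 9.0 | 30 |
| 30% | 12.4 | 9.25 | 9.0 | 8.5 | 7.0 | 30 |
| 50% | 14.0 | 8.75 | 8.3 | 7.5 | 5.0 | 30 |

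The total is constant: events move between cycles and none is lost. Middle cycles both lose and gain, so most of the visible change is at the two ends.

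**The case against.** The strongest reply is that very few events may be affected. The exposure is the first of four infusion days, from cycle 2 onward, and only where the time is blank. Protocol 7.2.1.2 asks for time of onset for every AE, Protocol 9.4 has missing data checked and queried, and Protocol 1.4 describes infusion-related reactions as infrequent. The analysis is descriptive, and AEs and reactions are also listed individually. All of this stands, and it keeps the point minor. It does not make the rule right, and listings do not correct a table.

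An AE that began before the infusion that day is correctly placed in the earlier cycle. Such onsets are plausible, since sites ask about problems since the previous visit. This also stands, and it means that a remedy sending every untimed event to the new cycle without exception would create the opposite error.

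A reader might infer that a fixed number of percentage points moves from each cycle to the one before. The documents do not support that: denominators are cycle-specific, cycle 1 loses nothing, middle cycles partly offset, and the tables count patients with at least one event, so a patient with another event in the same cycle does not leave its numerator. A reader might also infer that infusion-day reactions in general are misplaced. They are not; those after infusions 2 to 4, and after the first infusion of cycle 1, stay in their own cycle.

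**Conclusion.** The point holds as a narrow defect in a stated rule. An untimed AE dated on the first infusion day of cycle n (n ≥ 2) is allocated to cycle n-1. That is wrong whenever onset followed the infusion, and it conflicts with the SAP's own date-only definition of an infusion-related reaction. By-cycle AE and reaction tables and the onset day in period are affected.

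The size cannot be stated, because the documents give no missing-time rate; it may be close to zero. The illustration (10.8% against 9.0% in the first and last cycles at 10% missing, 12.4% against 7.0% at 30%) rests wholly on assumed inputs and, because it ignores patients with other events, is nearer an upper figure than an estimate for those inputs.

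It would be tempting to conclude that the primary safety result is biased. It is not: Protocol 3.1 defines the endpoint across the whole trial, and overall incidence and overall rates per patient-year are unchanged. Nor do the documents show that a false decline over cycles will appear, only that any distortion would tend that way. This is a low-severity point that is worth correcting because the correction is simple.

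**What to change.** Add one sentence to SAP 5.1.2: when the AE start date is complete, equals the date of the first infusion of cycle n, and only the time is missing, allocate the AE to cycle n, unless the available start or stop date/time or other recorded data show onset before the infusion. Keep the existing earliest-cycle rule for partial or missing dates, and record the change in SAP 6.3.

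The cost is that sentence and a small programming change. The downside is that some untimed AEs that truly began earlier that day will be counted in cycle n. Reporting the number of AEs reallocated under the sentence would show how much either choice matters.
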